the BARF and VAS scales. (4) The BARF and VAS scores associated with a patient's perception of the need for treatment. (5) The test - retest reliability of the VAS and BARF scores when nausea is rated as unchanged.

Section E: Protocol Risks/Subjects

E1. Risk Category

Category 1: Research not involving greater than minimum risk.

E2. Subjects

Gender:

Both

Age:

Adolescent (13-17 yrs), Child (3-12 yrs)

Ethnicity:

All Ethnicities

Primary Language:

Spanish

Groups to be recruited will include:

Patients

Which if any of the following vulnerable populations will be recruited as subjects?

Children

Vulnerable populations require special protections. How will you obtain informed consent, protect subject confidentiality, and prevent undue coercion?

Potential subjects will be identified from the surgery schedule at Texas Children's Hospital that is routinely available to Pediatric Anesthesiology for the purposes of case assignment. Parents of potential subjects will be approached by study staff in the waiting area prior to surgery. After the study is verbally explained, a written consent form will be provided and time given to allow consideration of study enrollment. The consent process will be conducted with emphasis on the voluntary nature of participation and that there is no direct benefit from enrollment. If the parents agree, a signed consent will be obtained along with a written assent from the child when age appropriate.

All research data will be kept secured and locked up in the office of the research co-ordinator. This office is located inside the office of the Department of Anesthesiology at Texas Children's Hospital. This office is only accessible by a personal digital access cards. Unauthorized individuals would not be able to enter these facilities. Any electronic data will be kept in password protected computers at the Texas Children's hospital, Department of Anesthesiology. The likelihood of such events is minimal.

E3. Pregnant woman/fetus

Will pregnant women and/or fetuses (as described in 45 CFR 46 Subpart B) be enrolled in the research?

No

E4. Neonates

Will neonates of uncertain viability or nonviable neonates (as described in 45 CFR 46 Subpart B) be enrolled in the research?

No

E5. Children

Will children be enrolled in the research?

Yes

Section F: Design/Procedure

F1. Design

Select one category that most adequately describes your research:

d) Questionnaire/survey/interview

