The power analysis was calculated conservatively for the following hypotheses:

Hypothesis 1: Nausea scores on the BARF and VAS scales would be lower in children after the administration of an antiemetic. A reduction in the VAS by 2 cms and by 1 face on a faces scale is considered a clinically important reduction in symptoms. (13) Assuming that the SD of nausea on the VAS scale in children is similar to that in adults (2.5 cm) (14), a sample size of 27 would have a 90% power at the 0.01 level of significance in detecting a 2.0 cm difference in the VAS following antiemetic therapy. Hypothesis 2: Children who received rescue antiemetics in the postoperative period will have higher postoperative nausea scores on the BARF and VAS scales than those who did not receive rescue antiemetics. In addition, children who required rescue antiemetics will have higher nausea scores at the time they received the rescue drug in the postoperative period than before they developed nausea. In other words, nausea scores in the postoperative period will be higher than scores prior to induction of anesthesia in children who received rescue antiemetics. (12) The power analysis for hypothesis 2 is similar to that for hypothesis 1, and a sample size of 27 would have a 90% power at the 0.01 level of significance in detecting a 2.0 cm difference in the VAS.

Hypothesis 3: There will be a good correlation between the BARF and VAS scores for nausea. A sample size of 127 would be estimated for an estimated maximum r of 0.8, a half-width of the confidence interval of ± 0.1 at an alpha of 0.01. (15) These estimates of r are in keeping with previous studies of the correlation between

pain scores on the VAS and the FPS-R scales. (6)

Allowing for a 10% rate of dropouts and incomplete data, we plan to recruit 240 patients in the preoperative area for the study to obtain data to test all hypotheses.

G2. Data Analysis

Provide a description of your plan for data analysis. State the types of comparisons you plan (e.g. comparison of means, comparison of proportions, regressions, analysis of variance). Which is the PRIMARY comparison/analysis? How will the analyses proposed relate to the primary purposes of your study?

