Visual analogue scores for pain and for nausea, and FPS-R scores for pain and BARF scores for nausea will be examined for normal distribution by the Kolmogorov-Smirnov test, but it is anticipated that the distribution will not be normal. Descriptive statistics (mean, median, standard deviation, and frequency distribution) of the nausea and pain scores will be obtained. The incidence of postdischarge nausea will be determined from the responses recorded in the diary and in the follow up phone call. The construct validity of the BARF scale would be assessed using the assumption that antiemetics reduce nausea and therefore nausea scores would be lower in children after the administration of an antiemetic (hypothesis 1). A subgroup of patients who received rescue antiemetics in the PACU will be examined. The pretreatment and post treatment VAS scores for nausea and BARF scores will be compared using a Wilcoxon test for non Gaussian distributed data. A reduction of scores by 2 cm on the VAS scale for nausea is traditionally accepted as a clinically satisfactory therapeutic response. A significant reduction in the BARF scores by 1 face in such patients will be accepted as construct validation. Content validity would be assessed by testing the hypothesis is that children with nausea will score higher on these scales than children without nausea (hypothesis 2). We will compare the postoperative nausea scores in patients who received rescue antiemetic therapy with the scores in patients who did not require this therapy using the Mann Whitney test. In addition, we will compare preoperative and postoperative BARF and VAS scores for nausea in patients who received antiemetics, making the assumption that healthy children will be free from nausea in the preoperative area. The Wilcoxon test for non Gaussian distributed data will be used for this comparison. Convergent validity would be tested by examining the correlation between BARF and VAS scales for nausea using the Spearman's Rho test. The hypothesis tested is that there would be a good correlation between the two scales (hypothesis 3). Discriminant validity would be tested by examining the relationship between pain and nausea. The hypothesis tested is that there would be a poor correlation between pain and nausea scores, particularly after the administration of opioids for analgesia (hypothesis 4). The correlation between (1) VAS scores for pain and nausea and (2) pain scores using the FPS-R scale and nausea scores using the BARF scale will be determined. Discriminant validity would be accepted if the correlation between these scores is not as good as the correlation between (a) VAS score for pain and the FPS score, (b) VAS score for nausea and the BARF score. A subgroup of patients who received analgesic therapy in the PACU will be examined. The correlation between the change in pain scores and nausea scores with analgesic treatment will be examined using the Spearman's Rho test. We can anticipate that there will be some correlations between nausea and pain as patients with pain often have concomitant nausea. However, satisfactory treatment of pain with opioids may not reduce nausea but even increase it, as nausea is a side effect of such therapy. Similarly, the correlation between the change in pain scores and nausea scores with antiemetic treatment will be examined using the Spearman's Rho test. The hypothesis tested will be accepted if the correlation of VAS and FPS-R scores will differ from the correlation between VAS scores for nausea and BARF scores. P values below 0.05 will be considered statistically significant. The minimum clinically relevant change in BARF and VAS scores for nausea will be determined by calculating the change in scores for patients who rated their nausea to be a little better than before or a little worse than before. Similarly, the scores at which a patient felt the need for rescue therapy would be determined in those subjects who responded positively to a question "Do you want any treatment for your nausea?" This will provide the threshold score for patient perception of the need for rescue therapy. The first and subsequent scores obtained from subjects who rated their symptoms as "no change from before" will be examined using an intra-class coefficient >0.7 as the criterion for test / retest reliability.

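### Test-retest reliability is declared when the sample ICC exceeds 0.7, with no confidence interval and no stated form of ICC, in a subset whose size the plan does not give

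*Combined protocol and SAP*

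**What the plan says.** Section D lists as objective 5 "The test - retest reliability of the VAS and BARF scores when nausea is rated as unchanged". The analysis is one sentence at the end of section G2. It begins "The first and subsequent scores obtained from subjects who rated their symptoms as" unchanged and says that these scores "will be examined using an intra-class coefficient >0.7 as the criterion for test / retest reliability". The sentence does not say whether the ICC is one-way or two-way, or whether it measures consistency or absolute agreement. It gives no confidence limit and no check of the mean difference between occasions.

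G2 sets a general significance level ("P values below 0.05 will be considered statistically significant") but does not tie it to the ICC. Of the score distributions it says that "it is anticipated that the distribution will not be normal".

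Section G1 gives sample sizes for hypotheses 1 to 3 only, then says that "we plan to recruit 240 patients in the preoperative area for the study to obtain data to test all hypotheses". It does not state how many children are expected to report no change.

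**The concern.** The rule compares a point estimate with 0.7. Sampling error in an ICC is large when the subset is small, and the plan leaves the size of this subset open. A scale whose true reliability lies below the plan's own bar could be reported as reliable, and a reader would have no interval from which to judge.

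The second gap is the unnamed form. In children who say that nothing changed, a systematic movement of the scores is a measurement failure. Absolute-agreement and one-way ICCs penalise such a movement; a consistency ICC does not. With the form open, the answer to objective 5 could depend on a choice made after the data are seen.

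**Working it through.** **Inputs from the documents**
- Criterion: ICC above 0.7 (G2).
- SD of nausea on the VAS: 2.5 cm (G1: "Assuming that the SD of nausea on the VAS scale in children is similar to that in adults (2.5 cm").
- Size of shift used as the extreme case: 2 cm (G1: "A reduction in the VAS by 2 cms and by 1 face on a faces scale is considered a clinically important reduction in symptoms").
- Recruitment 240 with 10% loss (G1), so at most 240 × 0.9 = 216 evaluable children.

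**Assumptions, not in the documents**
- Number of unchanged children: 20 to 216.
- Two ratings per child and normal scores. G2 expects non-normal scores, so the percentages are illustrative, and more so for the discrete BARF scale.

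**The plan's own figures.** There is none for the ICC. The G1 sample sizes do reproduce. A paired t-test with 2.0/2.5 = 0.8, two-sided alpha 0.01 and 90% power gives 26.6, so 27. For r = 0.8 at n = 127, Fisher's z gives a 99% interval of 0.700 to 0.869, whose lower limit is 0.1 below r.

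**Step 1: chance of passing.** With two ratings, a single-measure ICC corresponds to F = (1 + ICC)/(1 − ICC). When the true value is ρ, the observed F is distributed as (1 + ρ)/(1 − ρ) times a central F on n − 1 and n − 1 degrees of freedom. Passing needs an observed F above 1.7/0.3 = 5.667.
- ρ = 0.60: the multiplier is 1.6/0.4 = 4, so the central F must exceed 5.667/4 = 1.417.
- ρ = 0.65: the multiplier is 1.65/0.35 = 4.714, so it must exceed 1.202.
- ρ = 0.70: it must exceed 1, which happens half the time at any n.

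| Unchanged children | Pass if true 0.60 | Pass if true 0.65 | Pass if true 0.70 |
|---|---|---|---|
| 20 | 23% | 35% | 50% |
| 30 | 18% | 31% | 50% |
| 50 | 11% | 26% | 50% |
| 100 | 4% | 18% | 50% |
| 216 | 0.5% | 9% | 50% |

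**Step 2: interval around a bare pass.** An observed ICC of 0.71 gives F = 1.71/0.29 = 5.897. At n = 30 the 97.5% point of F on 29 and 29 degrees of freedom is 2.101. The limits on the F scale are 5.897/2.101 = 2.807 and 5.897 × 2.101 = 12.39. Converting back with (F − 1)/(F + 1) gives 0.47 to 0.85.

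**Step 3: effect of a uniform shift s, if a consistency form were used.** Take a consistency ICC of 0.80. The absolute-agreement ICC is 0.80 × 2.5² / (2.5² + s²/2) = 5/(6.25 + s²/2).
- s = 0.5 cm: 5/6.375 = 0.78
- s = 1 cm: 5/6.75 = 0.74
- s = 2 cm: 5/8.25 = 0.61

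It equals 0.7 when s² = 2 × (5/0.7 − 6.25) = 1.786, so s is about 1.34 cm. The consistency ICC stays at 0.80 throughout.

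**The case against.** - **A reader might infer that the plan lets a drifting scale pass. The text does not go that far.** It leaves the form unstated and does not choose consistency. An absolute-agreement or one-way ICC fits the sentence equally well and would penalise a shift. The documents predict no drift, and shifts of 0.5 or 1 cm leave the absolute-agreement ICC above 0.7 in the example. What stands is that the form is unspecified.
- **A reader might infer that the subset will be small. Nothing in the documents says so.** Section F2 schedules an assessment when the child is awake in the PACU and another before discharge, so many of the 216 could qualify. At that size a true ICC of 0.60 almost never passes. A true 0.65 still passes 9% of the time, and the expected number is still not stated.
- **The percentages assume normality, which the plan doubts.** This is correct. They show an order of magnitude and do not forecast this study.
- **Requiring the lower limit to exceed 0.7 would be a much harder bar.** At n = 30 it needs an observed ICC of about 0.85. That is a debatable trade-off and should not be imposed.
- **Objective 5 is the last of five in a minimal-risk questionnaire study, and the gap can be closed at analysis.** This limits the weight of the point. It also means that closing the gap costs little.

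**Conclusion.** The concern holds in a limited form. G2 sets a pass rule on a point estimate, with no interval and no named form, in a subset that G1 does not size. Nothing elsewhere in the documents supplies these.

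How much this matters depends on the unknown number of unchanged children. For a clearly substandard scale (true ICC 0.60), the chance of a false pass runs from about one in four at 20 children to about one in 200 at 216. For one just below the bar (0.65), it runs from about one in three to about one in eleven. These figures rest on two ratings per child and normal scores.

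The risk from a shift is conditional. It arises only if a consistency form is used and, in the worked case (consistency ICC 0.80, SD 2.5 cm), only when the shift exceeds about 1.3 cm. The point affects what objective 5 can conclude. It does not affect hypotheses 1 to 3 or patient care.

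**What to change.** In the G2 sentence on test-retest reliability:
- specify the two-way, absolute-agreement, single-rating ICC, for the VAS and the BARF separately;
- report it with a 95% confidence interval bootstrapped by child, since non-normal scores are expected;
- report the mean difference between first and later scores and the number of unchanged children beside it;
- keep 0.7 as the reference value, but describe reliability above 0.7 as not established with confidence when the interval includes 0.7.

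This needs SAP wording and a few lines of code, with no new data and no extra assessments.

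The downside is that the conclusion will often be qualified. With a true ICC of 0.80, the lower limit of a two-sided 95% interval exceeds 0.7 when a central F exceeds (5.667/9) times its 97.5% point. Under the same normal-score assumption that happens in about 23%, 36%, 63% and 92% of studies at n = 30, 50, 100 and 216. A qualified statement with its interval is still more informative than an unqualified pass.
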